**INTRODUCTION**

Note: in this document, any text taken directly from the non-interventional (NI) study protocol is *italicised*.

*In December 2019, COVID-19 was identified as a new, potentially fatal, respiratory infection caused by the novel coronavirus, SARS-CoV-2. The WHO declared COVID-19 a Public Health Emergency of International ConcernError! Reference source not found. on 30 January 2020 and further characterized the disease outbreak as a pandemic on 11 March 2020.Error! Reference source not found. As of 01 January 2022, more than 289,000,000 cases have been confirmed worldwide, and at least 5,440,154 deaths have occurred.Error! Reference source not found. Despite widespread use of COVID-19 vaccine since 2020 in Bahrain, COVID-19 caused 702830 cases, 26194 hospitalizations and 1546 deaths during the period 2020-2023 in Kingdom of Bahrain.*

*The clinical presentation of COVID-19 varies widely, ranging from an asymptomatic infection to critical illness characterized by respiratory failure, septic shock and other multiple organ dysfunction or failure.Error! Reference source not found. Although the majority of cases are asymptomatic or mild,Error! Reference source not found. patients who are hospitalized with COVID-19 may have significant morbidity and mortality.Error! Reference source not found.Error! Reference source not found. Between February 2020 and September 2021, the United States CDC estimated that of a total of 146.6 million infections, 85% of patients were symptomatic and only 5% required hospitalization for treatment.Error! Reference source not found.*

*According to the NIH guidelines, management of non-hospitalized patients with acute COVID-19 should include supportive care, advise on when to contact a health care provider and seek an in-person evaluation, and COVID-19 specific therapy for patients who have a high risk of disease progression.Error! Reference source not found. More specifically, non-hospitalized patients with mild-to-moderate COVID-19 who are at high risk of clinical progression may receive (listed in order of preference) nirmatrelvir (PF-07321332)/ritonavir (PaxlovidTM), sotrovimab, remdesivir, or molnupiravir.Error! Reference source not found.*

***Kingdom of Bahrain:***

*Kingdom of Bahrain is one of the leading countries in COVID-19 outpatient treatment care. A unique outpatient clinic has been established in May 2021 to provide outpatient care for patients with positive Coronavirus. Treatment including monoclonal antibodies such as Bamlamivimab, Regen-Cov, Sotorovimab and PaxlovidTM are offered for all high-risk and close contact patients, such treatments are in line with the guidelines of the FDA.*

*The clinic has a dedicated call center providing different services to ease the patient treatment process and provides follow-up care. The overall aim of the clinic is to target mild to moderate high risk COVID-19 patients and provide outpatient treatment as early as possible to reduce disease progression, including hospitalization and death.*

*On 01 January 2022, the National Health Regulatory Authority (NHRA) approved the emergency use of Paxlovid™ for mild-moderate cases who are at high risk – identified as per WHO definition of high-risk group – of developing severe COVID-19. Since approval, Paxlovid™ has been established as the first line therapy along with Sotrovimab in the Kingdom of Bahrain.*

*In the EPIC-HR trial, Paxlovid™ reduced the risk of hospitalization or death by 88% compared to placebo in non-hospitalized adults with laboratory-confirmed SARS-CoV-2 infection and a risk factor for progression to severe disease, when treatment was initiated within 5 days of symptom onset.Error! Reference source not found.Error! Reference source not found. Other efficacies reported for COVID-19 therapies, include sotrovimab (ie, 85% relative reduction reported),Error! Reference source not found.Error! Reference source not found. and remdesivir (ie, 87% relative reduction reported)Error! Reference source not found.Error! Reference source not found. and molnupiravir (ie, 30% relative reduction reported).Error! Reference source not found.Error! Reference source not found. Furthermore, in vitro analyses, suggested that Paxlovid™ is active against the B.1.1.529 (Omicron) variant of concern (VOC).Error! Reference source not found.*

*COVID-19 has put significant pressure on the healthcare system worldwide and caused an enormous economic burden to society. While patient characteristics, healthcare resource utilization (HRU) and healthcare costs of patients hospitalized with COVID-19 have previously been described in US studies,Error! Reference source not found.-Error! Reference source not found. such data are limited among non-US countries.Error! Reference source not found.Error! Reference source not found. Furthermore, while the majority of current research focuses on hospitalized COVID-19 patients, little is known about COVID-19 patients identified in an outpatient setting.*

*The availability of antiviral treatments in the outpatient setting, such as Paxlovid™, have potential to complement vaccination strategies during the COVID-19 pandemic and further reduce the burden on healthcare system capacity in the short- and long-term. There is a need to identify patients in the real-world setting globally, who are diagnosed with COVID-19 and may be at an increased risk of healthcare resource utilization, as prior literature suggests these patients are most likely to benefit from outpatient therapies. With the authorization (ie, EUA) of Paxlovid™, there is also a growing need to complement clinical trial findings and address data gaps by generating real-world evidence that may help inform healthcare decision-making globally during this early EUA utilization phase.*

*This study aims to describe the characteristics, outcomes and treatment patterns of COVID-19 patients, who are receiving Paxlovid™ in Bahrain according to the local drug label.*

## 1.1 STUDY DESIGN

This study is a retrospective cohort study examining COVID-19 patients who were treated with Paxlovid. It will also include a control group of COVID-19 patients who were offered, but refused, Paxlovid. It will involve a secondary data analysis of patient data from the ISeha electronic medical records.

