## **9. RESEARCH METHODS**

### **9.1. Study Design**

This will be a retrospective observational cohort study of patients diagnosed with COVID-19 in the Kingdom of Bahrain. Treated patients are defined as those have been prescribed nirmatrelvir, ritonavir and managed in the outpatient setting (eg, receiving medical treatment without being admitted to a hospital for COVID-19) while control group is those not treated with nirmatrelvir, ritonavir. Data will be from the *I-Seha electronic medical records* and descriptive analyses will be conducted for these two cohorts and will compare healthcare resource use in patients treated with nirmatrelvir, ritonavir and those not treated with nirmatrelvir, ritonavir.

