**Table 1. Cohort Definitions**

Name	Criteria	Identification Period	Index Date	Follow Up Period
Treated patients	Patients diagnosed with COVID-19 and treated with Paxlovid™	After Paxlovid™ availability during the same dominant variant (ie, Omicron or Delta etc.) era timeframe as Cohort	Paxlovid™ prescription written date or dispense date*  If neither of the above are available, the COVID-19 diagnosis date may be used as the index date	28 -days follow up
Control group	Patients diagnosed with COVID-19 and not treated with Paxlovid™	After Paxlovid™ availability during the same dominant variant (ie, Omicron or Delta etc.) era timeframe as Cohort	Date of COVID-19 diagnosis	28 -days follow up

\*If both dates are available in the data source, the most recent date should be used as the index date for Cohort.

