## 9.2. Setting

### 9.2.1. Inclusion Criteria

- Patients must meet all of the following inclusion criteria to be eligible for inclusion in the study: Age 18 years and older
- Patients with a diagnosis of COVID-19 whose information can be extracted from the I-Seha database

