### 9.2.2. Exclusion Criteria

**There are no exclusion criteria for this study.**

## 9.3 Variables

The following variables are used to obtain comprehensive descriptive results.

1. Demographics
2. Date of symptoms
3. Viral variant analysis where available (type of viral variant ie, omicron, delta etc.)
4. PCR date along with CT Value

5. Co-morbidities and
6. BMI if  $\geq 30$
7. Symptoms at presentation
8. COVID 19 vaccine status (NB 92% of population has been vaccinated -with at least one dose of COVID 19 vaccine- in Bahrain)
9. Hospital admission
10. Follow up looking at compliance and reason of non-compliance
11. Day 5,7, 21 and 28 symptoms for COVID-19 patients who receive and HRU limited to admission (ICU, ward, need for oxygen therapy) or death
12. Date of symptoms resolution if applicable

**Table 2** Table 2 below depicts the patient demographics that will be accessed during the baseline and follow-up periods. The baseline period is defined as one year before the index date. Comorbidities (full list in [Table 6](#)) and maintenance medication usage for chronic conditions (eg, statins, antihypertensives, etc.) will be described during the baseline period and follow-up periods and are listed in [Table 3](#).

Risk factors for severe COVID-19, intensive care unit (ICU) usage, invasive mechanical ventilation (IMV) usage, supplemental oxygen use, non-invasive ventilation, and high-flow nasal cannula usage are depicted in [Table 5](#) and will be extracted from the *I-Seha* national electronic health record database.

Where applicable, emerging treatment patterns may be assessed as the time from symptom onset to COVID-19 diagnosis, time from symptom onset to treatment initiation, and the time from COVID-19 diagnosis to treatment initiation as illustrated in [Table 5](#).

10Nov23 WHO recommendations for Paxlovid treatments to define: 1. COVID-19 patients who meet the WHO criteria for “strongly recommended” 2. COVID-19 patients who meet the WHO criteria for “conditionally recommended”, and 3. COVID patients who are not falling into categories 1 or 2 will be used.

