#### **9.4. Data Sources**

There is a database of all patients who were eligible for Paxlovid™ therapy and details of those that accepted Paxlovid™ therapy and those that did not. Between 16 February 2022 and 30 November 2022, there were 8263 patients that met all study inclusion and exclusion criteria eligible for Paxlovid™ therapy of whom at least 3000 patients were treated with Paxlovid™ therapy and 1000 were not. All records from the participant cohort of 8263 will be reviewed.

Data on these patients that were treated with Paxlovid™ therapy and those that did not will be extracted from the I-Seha Electronic Health Record (EHR). I-Seha EHR will be used to collect the variables listed below including: medical, biochemical and pharmacy data, HER data, and patient registry data. The I-Seha EHR data contains unstructured data that will be anonymized. I-Seha uses a large, geographically diverse administrative claims dataset which comprises patients served by a number of different health systems, providers and benefit structures. Complete information regarding all healthcare utilization submitted for payment is included in database.

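### Protocol and SAP define the control group differently, and the SAP reopens its own definition, so the HRU comparison can depend on who counts as a control

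*SAP*

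**What the plan says.** **Protocol, cohort definitions.** Section 9.1 states that the "control group is those not treated with nirmatrelvir, ritonavir". Table 1 has "Patients diagnosed with COVID-19 and not treated with Paxlovid™". Inclusion (9.2.1) is adult age plus "Patients with a diagnosis of COVID-19 whose information can be extracted from the I-Seha database", and 9.2.2 adds: "There are no exclusion criteria for this study". In 9.1 the setting condition, "managed in the outpatient setting (eg, receiving medical treatment without being admitted to a hospital for COVID-19", is attached to treated patients only.

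**Protocol, data source.** Sections 9.4 and 9.4.1 are narrower. They draw on a database of patients eligible for Paxlovid, with "details of those that accepted Paxlovid™ therapy and those that did not". Sections 9.4 and 9.5 give 8263 eligible patients, at least 3000 treated and 1000 not. None of these sections says that every control was offered treatment, or that controls were outpatients.

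**SAP.** Section 1.1 defines controls as "COVID-19 patients who were offered, but refused, Paxlovid". The Study population paragraph requires an outpatient setting and an offer for all patients and expects about 1000 refusers. Sections 1.12, 1.13 and 7.2.3 use the same comparison. However, the group variable in SAP Table 1 records only whether Paxlovid was received, and section 1.5 sets the full analysis set at about 8263.

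**Early admissions.** Protocol Tables 4 and 5 and SAP Table 4 leave out events within 24 hours of starting Paxlovid. No counterpart is given for controls, whose index date (Protocol Table 1) is the date of diagnosis.

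**The concern.** Not treated and offered-but-refused are different populations. An eligible patient may go untreated because nobody offered the drug, because it was unsuitable, or because the patient was already in hospital. These reasons carry different admission risks.

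The definition matters because Protocol 9.1 announces a comparison of healthcare resource use. SAP 1.13 and its Table 7 shell attach p-values, confidence intervals and effect sizes to hospitalization, ICU and oxygen outcomes.

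Two features make the gap consequential:

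- Under the protocol wording, a control diagnosed on admission counts as hospitalized from index, whereas a treated patient must have been managed without admission. The 24-hour exclusion does not catch that control, because it is timed from a drug the control never took.
- Two programmers could build different control columns from the same SAP. One following the Study population paragraph would use about 1000 refusers. One following Table 1 and section 1.5 could place every untreated patient among the 8263 in that column.

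**Working it through.** **1. The plan's own counts**

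Inputs: 8263 eligible, at least 3000 treated and 1000 not treated (Protocol 9.4 and 9.5); about 3000 treated, said to be about 53% of the eligible (SAP, Study population).

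- 3000 / 8263 = 36.3%, not 53%. Conversely, 0.53 × 8263 = 4379 treated, and 3000 / 0.53 = 5660 eligible. The 53% does not reproduce from 3000 and 8263.
- 3000 + 1000 = 4000, so 8263 − 4000 = 4263 patients (51.6%) are in neither named group.

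**2. Possible size of the control group**

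| Reading | Controls |
|---|---|
| Offered and refused (SAP 1.1, Study population) | about 1000 |
| Untreated among the 8263, if 53% were treated | 8263 − 4379 = 3884 |
| Untreated among the 8263, if exactly 3000 were treated | 8263 − 3000 = 5263 |

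The last figure is an upper bound, because at least 3000 were treated.

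**3. What the definition can do to the result with no drug effect**

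The documents' WHO risk groups (Protocol 9.7) give hospitalization rates of 6%, 3% and 0.5% without stating a time window. I use 3% as the follow-up risk in the treated group and in ordinary controls. The shares below are assumptions; the documents give none.

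(a) A share f of controls is already in hospital at index. Control risk = f + (1 − f) × 0.03; RR = 0.03 / control risk.

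| f | Control risk | Apparent RR |
|---|---|---|
| 1% | 3.97% | 0.76 |
| 2% | 4.94% | 0.61 |
| 5% | 7.85% | 0.38 |

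At f = 2%, with 3000 treated and 1000 controls, the difference is 3.00% − 4.94% = −1.9 points (95% CI −3.4 to −0.5). The chance of a falsely significant benefit is about 80%, taking the SAP's alpha of 0.05 as two-sided.

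(b) A share g of controls is low risk at 0.5%. Control risk = g × 0.005 + (1 − g) × 0.03.

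| g | Control risk | Apparent RR |
|---|---|---|
| 25% | 2.38% | 1.26 |
| 50% | 1.75% | 1.71 |

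(c) The 1000 refusers at 3% are pooled with the other 4263 at rate r (the upper-bound reading). Control risk = (1000 × 0.03 + 4263 × r) / 5263.

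| r | Control risk | Apparent RR |
|---|---|---|
| 0.5% | 0.98% | 3.08 |
| 3% | 3.00% | 1.00 |
| 6% | 5.43% | 0.55 |

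The choice of controls alone can produce an apparent benefit, no difference or an apparent harm.

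**The case against.** The strongest reply is that the documents, read together, mostly mean the same thing. Several parts of it stand.

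- **Eligibility.** From Protocol 9.1 and Table 1 alone, a reader might infer that anyone with COVID-19 and no Paxlovid, eligible or not, becomes a control. Sections 9.4, 9.4.1 and 9.5 do not support that: the source is a database of eligible patients. Accepting or not accepting also comes close to being offered and refusing, though the protocol never says that every control had an offer.
- **Size.** A reader might infer that the protocol plans 5263 controls. It does not; 9.5 states 1000 untreated, the same as the SAP. The larger figure arises only if the unclassified 4263 were all untreated.
- **Outpatient setting.** The SAP's Study population paragraph applies the outpatient and offer conditions to both groups, and Protocol 9.7 allows the SAP to modify the protocol. On that paragraph, a patient diagnosed on admission should not be a control. But the SAP does not flag the change, does not spell out not being admitted at or before index, and reopens the definition in its Table 1 and section 1.5.
- **Direction.** A reader might infer that the bias must favour Paxlovid. That holds for controls already in hospital, but lower-risk or never-offered controls push the other way.
- **Status of the comparison.** The primary objective is descriptive, resource use is secondary, Protocol 9.9 disclaims causality and the SAP calls the work exploratory. This lowers the severity, but between-group tests are still planned.

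Propensity matching (SAP 1.13) does not settle the matter. Its list contains neither setting at diagnosis nor offer status, it depends on data availability, and section 1.11 marks covariates as not applicable.

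**Conclusion.** The plan is wrong as written and should be fixed. The protocol's cohort definitions and the SAP describe different control groups, and the SAP's own group variable and full analysis set do not hold to its definition. Controls could number about 1000 or, as an upper bound, 5263, with about 4263 patients unassigned.

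The documents establish the ambiguity and the one-sided early-admission rule. They do not establish how large the bias would be or which way it would run. The risk ratios of 0.38 to 0.76 and 1.26 to 1.71 rest on assumed shares and a common 3% risk; they show how sensitive the comparison is and do not predict its result.

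**What to change.** - State one control definition (eligible, offered, refused, outpatient and not admitted at or before index) in Protocol 9.1, Table 1 and 9.2.1, and in the SAP's Study population, section 1.5 and Table 1 group variable.
- Apply the same outpatient, not-admitted-at-index condition to treated patients. Tying it to index also makes clear that later admission does not remove a treated patient from the cohort.
- Reword the early-admission exclusion in Protocol Tables 4 and 5 and SAP Table 4 so that it runs from the index date in both groups.
- Report the remaining eligible patients in a separate descriptive column, and add a flow table that accounts for all 8263. Reconcile the 53% figure there.

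The cost is wording in both documents plus one flow table. The control group may fall slightly below 1000 once patients admitted at or before index are removed. Refusers may still differ from acceptors, for example in severity, vaccination or care seeking, so residual confounding remains and the report should say so.

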### **Study population**

Patients will be eligible for inclusion in the study if they were diagnosed with COVID-19 between February and November 2022, were treated in an outpatient setting in the Kingdom of Bahrain, and were offered Paxlovid. Paxlovid was offered to patients in the Kingdom of Bahrain if they were at high risk of complications from COVID-19 due to age  $\geq$  50 years, BMI  $\geq$  35, or a medical history of chronic kidney disease (eGFR  $\geq$ 30 ml/min), diabetes mellitus, primary or secondary immunosuppressive disease or receiving immunosuppressive treatment, cardiovascular disease or hypertension, chronic lung diseases, sickle cell disease, neurodevelopmental disorders, or having a medical-related technological dependence. There are no exclusion criteria.

EHRs from approximately 3000 COVID-19 patients who were treated with Paxlovid, all of whom gave verbal consent for treatment that was recorded in the medical record, will be included in the study. These patients were treated between February and November 2022, and consist of approximately 53% of the total eligible patient population from the timeframe. A comparison group of patients will also be included. This group will consist of approximately 1000 patients with COVID-19 that were offered Paxlovid therapy but who refused treatment, over this same time period.

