## Kingdom of Bahrain:

Kingdom of Bahrain is one of the leading countries in COVID-19 outpatient treatment care. A unique outpatient clinic has been established in May 2021 to provide outpatient care for patients with positive Coronavirus. Treatment including monoclonal antibodies such as Bamlamivimab, Regen-Cov, Sotorovimab and Paxlovid™ are offered for all high-risk and close contact patients, such treatments are in line with the guidelines of the FDA.

The clinic has a dedicated call center providing different services to ease the patient treatment process and provides follow-up care. The overall aim of the clinic is to target mild to moderate high risk COVID-19 patients and provide outpatient treatment as early as possible to reduce disease progression, including hospitalization and death.

On 01 January 2022, the National Health Regulatory Authority (NHRA) approved the emergency use of Paxlovid™ for mild-moderate cases who are at high risk – identified as per WHO definition of high-risk group – of developing severe COVID-19. Since approval, Paxlovid™ has been established as the first line therapy along with Sotrovimab in the Kingdom of Bahrain.

In the EPIC-HR trial, Paxlovid™ reduced the risk of hospitalization or death by 88% compared to placebo in non-hospitalized adults with laboratory-confirmed SARS-CoV-2 infection and a risk factor for progression to severe disease, when treatment was initiated within 5 days of symptom onset. Other efficacies reported for COVID-19 therapies, include sotrovimab (ie, 85% relative reduction reported), and remdesivir (ie, 87% relative reduction reported) and molnupiravir (ie, 30% relative reduction reported). Furthermore, *in vitro* analyses, suggested that Paxlovid™ is active against the B.1.1.529 (Omicron) variant of concern (VOC).

COVID-19 has put significant pressure on the healthcare system worldwide and caused an enormous economic burden to society. While patient characteristics, healthcare resource utilization (HRU) and healthcare costs of patients hospitalized with COVID-19 have previously been described in US studies, such data are limited among non-US countries. Furthermore, while the majority of current research focuses on hospitalized COVID-19 patients, little is known about COVID-19 patients identified in an outpatient setting.

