## 9.5. Study Size

This is a retrospective observational study using a sample afforded by the I-Seha Electronic health record. While this study will be descriptive in nature, feasibility queries show that, between 16 February 2022 and 30 November 2022, there were 8263 patients that met all study inclusion and exclusion criteria eligible for Paxlovid™ therapy of whom at least 3000 patients were treated with Paxlovid™ therapy and 1000 were not. All records from the participant cohort of 8263 will be reviewed.

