## 1.2 STUDY OBJECTIVES

The overall aim of this study is to examine the baseline demographic, clinical, and outcome characteristics of COVID-19 patients who received Paxlovid.

PFIZER CONFIDENTIAL

CT24-WI-GL03-RF03 2.0 *Non-Interventional Statistical Analysis Plan For Secondary Data Collection*  
*Study 01-Jun-2020*  
Page 6 of 22

The objectives are

- (i) to describe the demographic, clinical, and outcome characteristics of COVID-19 patients who received Paxlovid and COVID-19 patients who were offered, but refused Paxlovid
- (ii) to examine differences in the demographic characteristics (e.g., age, sex, nationality, type of outpatient encounter, vaccination status) between COVID-19 patients who received Paxlovid and COVID-19 patients who refused Paxlovid,
- (iii) to examine differences in the clinical characteristics (e.g., comorbidities, symptoms, duration of symptoms) between COVID-19 patients who received Paxlovid and COVID-19 patients who refused Paxlovid over a five-day follow-up,
- (iv) to examine differences in outcomes (e.g., hospitalisations, time spent in an intensive care unit, time spent with invasive mechanical ventilation, supplemental oxygen usage, re-admission to hospital, deaths) between COVID-19 patients who received Paxlovid and COVID-19 patients who refused Paxlovid over a five-day follow-up.
- (v) To examine differences in the proportion of COVID-19 patients who meet the most up-to-date WHO recommendations for the use of therapeutics in the treatment of COVID-19 (ie, version 14, published 10Nov2023) in comparison to Kingdom of Bahrain national recommendations.

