
Using these criteria, we will look at frequency and percentage of COVID-19 patients who will fall in those criteria to understand strongly recommended or conditionally recommended use of Paxlovid™ in comparison to the country of issue recommendations.

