**Table 8: Comparison of WHO and Bahrain national recommendation for Paxlovid Treatment in COVID-19 patients**

Outcome Variables	WHO recommendation for Paxlovid treatment		Bahrain national recommendation for Paxlovid treatment
	Strongly recommended	Conditionally recommended	Strongly recommended
All COVID patients			
Paxlovid group			
Control group			

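### Table 8 does not say which criteria fill its Bahrain column; if they are the list used to offer Paxlovid, that column is about 100% by selection

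*SAP*

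**What the plan says.** **Objective.** Secondary objective 1 (protocol Section 8) and SAP objective (v) set WHO version 14 against the national recommendations. The SAP wording begins "To examine differences in the proportion of COVID-19 patients who meet the most up-to-date WHO recommendations".

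**Entry.** SAP Study population requires that patients were offered Paxlovid, and explains the offer: "Paxlovid was offered to patients in the Kingdom of Bahrain if they were at high risk of complications from COVID-19 due to age" (50 years or over), a BMI threshold, or a listed medical history. The controls were also offered it, and refused. Protocol 9.4 says "There is a database of all patients who were eligible for Paxlovid™ therapy", and 9.5 says "there were 8263 patients that met all study inclusion and exclusion criteria eligible for Paxlovid™ therapy". Protocol 9.2.1 is wider: any adult with a COVID-19 diagnosis that can be extracted.

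**National criteria.** Besides the offer list, the background (protocol Section 7, repeated in the SAP Introduction) says national approval was for high-risk patients, "identified as per WHO definition of high-risk group".

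**Table.** The Table 8 shell compares WHO with the "Bahrain national recommendation for Paxlovid Treatment in COVID-19 patients". It has two WHO columns (strong, conditional), one Bahrain column, and rows for all COVID patients, the Paxlovid group and the control group. The SAP text after its Table 4 says the WHO groups will be used "to understand strongly recommended or conditionally recommended use of Paxlovid™ in comparison to the country of issue recommendations". Protocol 9.3 also requires a third WHO category, patients in neither; the shell has no column for it.

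**The concern.** A comparison of two sets of criteria is informative when patients can pass or fail either one. Here entry depends on having been offered the drug, and the offer is described as following a national risk list. If that list is also what Table 8 scores, one side of the comparison is settled before any data are read.

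A reader could then take the gap between the columns as a finding about national policy, for instance that Bahrain recommends treatment more widely than WHO. The study could not show the opposite, that national criteria are narrower than WHO's, because the patients who would show it were not offered Paxlovid and so are not in the data. Because the plan does not name the criteria, nobody can tell from Table 8 which situation applies.

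**Working it through.** **Plan's own figures.** The documents give no expected value for the Bahrain column. The only percentage stated for this population is that the roughly 3000 treated patients are about 53% of those eligible (SAP Study population). It does not reproduce: 3000/8263 = 36.3% and 3000/(3000 + 1000) = 75.0%; 53% implies 3000/0.53 ≈ 5660. The all-patients row therefore has three candidate denominators: 8263, about 5660 and about 4000. With 8263, about 8263 − 4000 = 4263 patients (51.6%) are in neither group row. The protocol says at least 3000 were treated, so 4263 is approximate.

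**Inputs.** W = share meeting a WHO recommendation, strong or conditional. e = share offered Paxlovid without meeting the list. Neither is in the documents; both are assumed.

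**Case A: the column scores the offer list.**
- Bahrain share B = 1 − e; difference = B − W.
- With e = 0, B = 100% (3000/3000 and 1000/1000 in the group rows; 8263/8263 in the all-patients row if that row is the eligible cohort). The difference is 1 − W: 50, 30 or 10 points for W = 50%, 70% or 90%. No patient can be WHO-yes and Bahrain-no.
- With e = 1%, 5% or 10% (83, 413 or 826 of 8263), B = 99%, 95% or 90%.
- Who is missing: a patient under 50 with chronic liver disease only is in the WHO moderate-risk group (protocol 9.7) but not on the offer list.
- Who is visible: a patient aged 50 to 65 with no other factor is on the offer list but not in the WHO moderate group, whose age limit is above 65.

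**Case B: the column scores something else, such as the WHO-based definition.**
- B is not tied to entry. The WHO-yes/Bahrain-no share c lies between max(0, W − B) and min(W, 1 − B). The share classified differently is (B − W) + 2c.
- B = 95%, W = 70%: c is 0 to 5 points; 25% to 35% are classified differently.
- B = 90%, W = 90%: the margins show no difference; c is 0 to 10 points; 0% to 20% are classified differently, up to 0.20 × 8263 ≈ 1653 patients.
- The margins would settle c only if one set of criteria lies inside the other, which cannot be judged until both are named.

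**The case against.** The strongest reply is that the plan never says Table 8 scores the offer list. That is correct. The WHO-based definition is a real rival, and under it the column need not be 100%. The SAP also says the drug was offered if the criteria were met, not only if. The background says treatments "are offered for all high-risk and close contact patients", although that sentence covers several treatments together and is weak evidence of off-list Paxlovid offers. Hence about 100%, and only under a stated condition.

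Two stronger readings are tempting.
- A reader might infer that the column is 100% in every row. The documents do not support this for the all-patients row: protocol 9.2.1 and protocol Table 1 define patients by diagnosis, and SAP 1.5 describes its 8263 by comorbidity, not as eligible or offered. Only protocol 9.4 and 9.5 call the 8263 eligible.
- A reader might infer that the differing BMI thresholds (30 in protocol Table 3 and 9.7, 35 in the SAP) pull the column below 100%. That would need entry at 30 and scoring at 35, which no section states; entry at 35 with scoring at 30 leaves it unchanged.

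It is also fair that the WHO share among offered patients is informative and already planned. With e = 0 the margins determine every cell, so a cross-table adds nothing there. The missing third category can be recovered by subtraction if the row N is shown. W and e are illustrations, and the 90%/90% example was chosen so that the margins cancel. The objective is descriptive, with no hypotheses. These points limit the size of the problem; they do not supply the missing definition.

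**Conclusion.** The point holds as a conditional and should be fixed before Table 8 is filled. The offer list is the only itemised Bahrain rule in either document. If it is scored, the Bahrain column is about 100% by selection in the Paxlovid and control rows, and in the all-patients row if that row is the 8263 eligible patients. The comparison then reduces to about 1 minus the WHO share and cannot show whether national criteria are narrower than WHO's. If the WHO-based definition is scored, that conclusion does not follow, but the shell's margins still leave the extent of disagreement unknown. Under either reading the shell omits the WHO category of neither that protocol 9.3 requires. The documents do not support saying outright that the objective is empty. Confidence is medium, because the plan does not settle which case applies.

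**What to change.** In this order:

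1. Name in the SAP the criteria that count as the national recommendation, reconciling the background's WHO-based definition with the list in SAP Study population. Give the denominator and N of each Table 8 row, reconciling protocol Table 1 and 9.2.1 with SAP Study population and SAP 1.5. State how the WHO risk groups map to strong and conditional. Reconcile the BMI 30 and BMI 35 passages.
2. If the criteria are the offer list, restate objective (v) and Table 8 as the number and percentage, with 95% confidence interval, in each WHO category (strong, conditional, neither) among patients offered Paxlovid, overall and by group. Drop the Bahrain column or label it as fixed by selection.
3. If the criteria differ from the offer list, or if all adult diagnoses are extracted, apply both sets to every patient and show the WHO-by-Bahrain cross-classified table.

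Cost: wording in the protocol and SAP and one table shell. New data are needed only if all adult diagnoses are extracted. Under step 2 the conclusion is limited to patients offered Paxlovid; the same limit applies under step 3 without the wider extract.
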